Various hypofractionated radiotherapy (HRT) regimens have been reported for the management of patients with early-stage NSCLC not amenable to surgery or SBRT, HRT is commonly implemented, but the optimal dose schedule has not been established. Selection of HRT dose has been informed by studies of HRT/stereotactic body radiotherapy (SBRT) which have established a direct correlation between BED and tumor control. 17,26 Generally speaking, RT doses with BED₁₀ > 100 results in significantly improved disease control when compared to doses with BED₁₀ < 100. For this reason, efforts to deliver various regimens of HRT that reach or approach a BED₁₀ of 100 Gy are of interest. A study conducted by the Cancer and Leukemia Group B (CALGB) 39904 protocol evaluated various HRT regimens to a total dose of 70 Gy in 17-29 fractions without concurrent chemotherapy for early stage T1-T2N0 NSCLC. In this Phase I study, disease control was favorable and no dose-limiting toxicity was observed.

For patients with NSCLC not amenable to SBRT, surgery or concurrent chemoradiotherapy, a commonly utilized HRT fractionation at our institution is 70.2 Gy in 26 fractions. This regimen has a BED $_{10}$ of 89.15 Gy. Recent data from our institution show that this fractionation results in favorable disease control and toxicity profiles. In our cohort, which included stage II patients and those with hilar (N1) nodal involvement, 96% were treated with 70.2 Gy in 26 fractions. The 3 year cumulative incidence of locoregional failure (including in untreated regional lymph nodes) was 32%, and only 2 (4%) of patients developed CTCAE version 4.0 Grade 3 radiation pneumonitis after treatment. No instances of Grade 3+ esophagitis occurred. Based on these data, a similar dose fractionation scheme of 70 Gy in 25 fractions (BED $_{10}$ = 89.6 Gy) is likely to have a 2 year local control rate of approximately 70%. In cases where PBT dose constraints cannot be met, the dose to the PTV within 1 cm of the

PBT will be reduced slightly to 67.5 Gy in 25 fractions (BED₁₀ = 85.73 Gy, BED₃ = 128.25 Gy) to reduce the risk of serious toxicity. A similar dose (66 Gy in 24 fractions, BED₁₀ = 84.15 Gy, BED₃ = 126.5 Gy) has been previously reported to be well tolerated with concurrent low dose daily cisplatin.⁹

Selection of Dose Constraints for the Proximal Bronchial Tree, Esophagus, and Heart

Proximal Bronchial Tree

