We plan to decrease bronchial toxicity risk in multiple ways. First, we will reduce the high dose level for the target area in close proximity to the PBT when dose constraints cannot be met. For these patients, a high dose level of 67.5 Gy in 25 fractions will be prescribed, which is nearly biologically equivalent to 66 Gy in 24 fractions, which has been reported to be safe when used in patients with Stage III NSCLC with daily cisplatin. Second, during construction of the RT plan, any overlapping proximal bronchial tree plus a 5mm uniform expansion (planning organ at risk volume or PRV) will be excluded from the high dose PTV. Second, we will provide dose constraints to bronchial structures (mandatory for maximal dose, and ideal for volumetric constraints) in a similar fashion to RTOG 0813. Finally, we will limit the maximum dose in the entire plan to no more than 115%, unlike the Nordic HILUS study, further reducing the risk of very high doses of radiation being delivered to the proximal bronchial tree due to intrafractional motion.

Esophagus

As with the proximal bronchial tree, late esophageal toxicity is of concern in high dose radiotherapy to the mediastinum and centrally located lung tumors. In RTOG 0813, esophagus adjacent to the target was limited to 105% of the prescription dose. They noted minimal late esophageal toxicity with doses up to 60 Gy in 5 fractions³ Additionally, in Alliance/CALGB 31102, the esophagus was limited to a maximal dose of 105% of the prescription, and a V55 Gy of under 30%, with no reported late Grade 3 or higher toxicity.³⁰ Furthermore, a recent normal tissue complication model of the esophagus developed based on patients treated with hypofractionated radiotherapy reported a 5% late high grade esophageal complication rate with a maximal EQD2₃ dose of 113.3 Gy.¹⁰ Based on these data, we will plan for mandatory esophagus constraints of 73.5 Gy (105% of prescription, EQD2₃ = 87.3 Gy)

and a V55 Gy under 30%. As with the bronchial tree, the esophagus plus a 5mm uniform expansion will be excluded from the high dose target volume.

Heart

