6.1.1 Radiation Therapy

Hypofractionated radiation therapy will be delivered to all patients. The prescribed dose will be 70 Gy in 25 fractions

- 1. Technical Factors and Radiation Planning
 - a. Radiation Dose Selection
 - i. The radiation dose for the high dose PTV was selected based on previous clinical experience with 70.2 Gy in 26 fractions, and decreasing the treatment course by one fraction, leading to a **high dose of 70 Gy in 25 fractions.** As this dose is likely not necessary for control of microscopic disease treated in the clinical target volume (CTV), a **lower dose CTV will be treated to 57.5 Gy in 25 fractions.** This lower dose was selected based on BED and EQ2D calculations, which can be used to compare doses using non-standard (ie non 1.8-2 Gy) fraction sizes (see Table 1).

ii.

Table 1. COMPARISON BED and EQD2 for Dose Fractionation Schemes				
Dose / Fractions	BED ₁₀ Gy (Tumor)	BED ₃ Gy (Normal Tissue)	EQD2 ₁₀ Gy (Tumor)	EQD23 Gy 2 (Normal Tissue)
60 Gy / 30 fx (SoC)	72	100	60	60
66 Gy / 30 fx	80.52	114.4	67.1	68.84
70.2 Gy / 26 fx	89.15	133.38	74.3	80.03
58.5 Gy / 26 fx	71.66	102.38	59.72	61.43
66 Gy / 24 fx	84.15	126.5	70.13	75.9
70 Gy / 25 fx	89.6	135.33	74.67	81.2
67.5 Gy / 25 fx	85.73	128.25	71.44	76.95
57.5 Gy / 25 fx	70.72	101.58	58.94	60.95

b. CT Simulation

- i. All patients will undergo CT simulation of the chest. The use of intravenous contrast with the CT simulation is not mandatory.
- ii. 4D-CT will be obtained for motion management. The use of abdominal compression or respiratory gating is encouraged.
- iii. Immobilization will be done with a customized vacuum sealed bag.
- c. Target Volume Definitions:

WFBCCC # 62220

- i. GTV = gross tumor (both primary and lymph nodes) on CT simulation. Lymph nodes > 1 cm in short axis diameter or with an SUV > 3 are considered to be involved unless proven negative by biopsy.
- ii. iGTV = GTV accounting for tumor motion on all phases of 4D CT
- iii. CTV 7000 = iGTV with no expansion
- iv. CTV_5750 = iGTV uniformly expanded by 5mm
 - 1. CTV_5750 can be excluded from normal structures without radiographic evidence of invasion (for example≤ vertebral bodies, chest wall, or ribs)
 - 2. CTV_5750 should not be excluded from the trachea, esophagus, proximal bronchial tree, or intrathoracic cardiovascular structures
- v. PTV_7000 = CTV_7000 uniformly expanded 5mm minus Esophagus_PRV, PBT_PRV, and Brachial Plexus PRV (if applicable)
- vi. PTV_5750 = CTV_5750 uniformly expanded by 5mm

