- vii. PTV 6750 = PTV 7000 minus PBT 1cm
 - PTV_6750 will only be delineated in cases where dose constraints for the PBT cannot be met
- d. Organs at Risk to be contoured
 - i. For all patients
 - 1. Bilateral lungs
 - 2. Spinal cord (5 cm above and below the PTV)
 - 3. Aorta (5 cm above and below the PTV)
 - 4. Esophagus (entire length)
 - 5. Esophagus PRV = Esophagus plus 5mm uniform expansion
 - 6. Heart (including the pericardial sac)
 - 7. Trachea/proximal bronchial tree
 - a. 5 cm superior to the PTV to the end of all main lobar bronchi
 - 8. PBT_PRV = trachea and proximal bronchial tree plus 5mm uniform expansion
 - ii. For patients with the PTV within 2 cm of the organ at risk*
 - 1. Brachial plexus
 - a. Only the major trunks of the brachial plexus need to be contoured
 - b. Left and right brachial plexuses should be contoured separately with generation of separate Brachial_Plexus_PRVs if the PTV is within 2 cm of both brachial plexuses
 - 2. Brachial_Plexus_PRV = Brachial plexus plus 5mm uniform expansion
 - 3. Chest wall (3 cm superior and inferior to the PTV)
 - 4. Ribs
 - 5. Stomach
 - 6. Liver
 - * if non-coplanar beams or arcs are used then all organs at risk must be contoured For patients who cannot meet PBT dose constraints
 - 1. PBT_1cm = trachea and proximal bronchial tree plus 1 cm uniform expansion iv.
 - Target Coverage Requirements
 - i. Mandatory
 - 1. 95% of PTV 5750 to at least 95% of prescription (54.63 Gy)
 - 2. 99% of PTV 5750 to at least 90% of prescription (51.75 Gy)
 - ii. Ideal

iii.

- 1. 95% of PTV 7000/6750 to at least 95% of prescription (66.5 Gy/64.13 Gy)
- 2. 100% of PTV 7000/6750 to at least 95% of prescription (66.5 Gy/64.13 Gy)
- 3. 95% of PTV_7000/6750 to at least 100% of prescription (70 Gy/67.5 Gy)
- 4. 99% of PTV 7000/6750 to at least 90% of prescription (63 Gy/60/75 Gy)
- 5. 100% of PTV 5750 to at least 95% of prescription (54.63 Gy)

- f. Organ at Risk Constraints
 - i. Mandatory
 - 1. Spinal Cord: $D0.03 \text{ cm}^3 < 45 \text{ Gy}$
 - 2. Esophagus: $D0.03 \text{ cm}^3 < 73.5 \text{ Gy}$;
 - 3. Lungs-GTV: V20 Gy \leq 35%;
 - 4. Proximal Bronchial Tree: D0.03 cm 3 < 73.5 Gy; D3 cm 3 < 66.25
 - 5. Heart D100% < 30 Gy
 - 6. Stomach: $D0.03 \text{ cm}^3 < 60 \text{ Gy}$
 - 7. Liver: Mean dose < 30 Gy; at least 700 cm³ of normal liver to < 15 Gy
 - 8. Maximum physical dose < 115% of high dose prescription
 - a. PTV_7000: maximum physical dose < 80.50 Gy
 - b. PTV 6750: maximum physical dose < 77.63 Gy

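### Section 6.1.1 defines the 67.5 Gy volume as target more than 1 cm from the airway, but section 1.0 assigns 67.5 Gy to target within 1 cm of it

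*Combined protocol and SAP*

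**What the plan says.** **Section 1.0, Selection of HRT Dose**, describes a local reduction: "In cases where PBT dose constraints cannot be met, the dose to the PTV within 1 cm of the" PBT is lowered to 67.5 Gy in 25 fractions.

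**Section 1.0, Proximal Bronchial Tree**, lists this first among its airway protections: "we will reduce the high dose level for the target area in close proximity to the PBT when dose constraints cannot be met". The next sentence is broader: "For these patients, a high dose level of 67.5 Gy in 25 fractions will be prescribed".

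**Section 6.1.1, Target Volume Definitions and Organs at Risk**, gives the instructions a planner follows:
- "PTV_7000 = CTV_7000 uniformly expanded 5mm minus Esophagus_PRV, PBT_PRV" (the brachial plexus PRV is also removed where applicable). PBT_PRV is the airway plus 5 mm.
- "PBT_1cm = trachea and proximal bronchial tree plus 1 cm uniform expansion".
- "PTV 6750 = PTV 7000 minus PBT 1cm".
- "PTV_6750 will only be delineated in cases where dose constraints for the PBT cannot be met".

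**Section 6.1.1, Organ at Risk Constraints**, lists as mandatory: "Proximal Bronchial Tree: D0.03 cm 3 < 73.5 Gy; D3 cm 3 < 66.25".

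**Section 6.1.1, Target Coverage Requirements and item g.iv**: mandatory coverage is set only for PTV_5750. Coverage of PTV_7000 and PTV_6750 is listed as ideal, and the treating physician may relax it if mandatory organ limits cannot be met.

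**The concern.** The background section and the planning section send the same reduced dose to different tissue. Section 1.0 puts it beside the airway. Section 6.1.1 cuts that tissue out of the volume that receives it. A planner working only from 6.1.1 would not reproduce the step-down that section 1.0 describes.

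The stake is the prescription to a thin band of target next to the structure the protocol most wants to protect. That band can contain gross tumor, and section 1.0 chose the doses on the argument that tumor control depends on BED. Section 11.4 expects accrual across several sites, so the definition should not depend on unwritten local understanding.

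**Working it through.** **1. The plan's own dose figures.** Appendix E gives BED = D(1 + d/(α/β)), with D the total dose and d the dose per fraction. All schedules use 25 fractions.
- 67.5 Gy, d = 2.7: BED10 = 67.5 × 1.27 = 85.725 (plan: 85.73); BED3 = 67.5 × 1.90 = 128.25 (plan: 128.25).
- 70 Gy, d = 2.8: BED10 = 70 × 1.28 = 89.60; BED3 = 70 × (1 + 2.8/3) = 135.33. Both match the plan.
- 57.5 Gy, d = 2.3: BED10 = 57.5 × 1.23 = 70.725 (plan: 70.72).

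The arithmetic in Table 1 and Appendix E is sound. The problem is which volume gets which dose.

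**2. The volumes, by distance x from the airway surface.**
- PBT_PRV covers x from 0 to 5 mm, so PTV_7000 has only x > 5 mm.
- PBT_1cm covers x from 0 to 10 mm.
- PTV_6750 under 6.1.1 is PTV_7000 without PBT_1cm: x > 10 mm.
- The 67.5 Gy region under section 1.0 is the part of PTV_7000 within 1 cm: 5 < x ≤ 10 mm.

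The overlap is empty. Some underscores were lost in the text, but the word for subtraction is intact, and the PTV_7000 definition uses it in the same sense.

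**3. When the band exists.** Let t be the distance in mm from the airway to the edge of the gross tumor including motion. Along one line, PTV_7000 begins at max(t − 5, 5) mm, so the band is non-empty when t < 15.
- t = 8: 5 mm of band, 2 mm of it gross tumor.
- t = 10: 5 mm of band, no gross tumor.
- t = 12: 3 mm of band.
- t = 15: none.

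Section 3.1.2.1 defines ultracentral disease by a distance of at most 1 cm, so every ultracentral patient has a band unless another PRV removes it. The rule applies only if the PBT limits also fail.

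**4. What each reading prescribes.**

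| Reading | Band, 5–10 mm | Beyond 10 mm |
|---|---|---|
| Section 1.0, Selection of HRT Dose | 67.5 Gy | 70 Gy |
| 6.1.1, PTV_6750 replaces PTV_7000 | 57.5 Gy (through PTV_5750) | 67.5 Gy |
| 6.1.1, PTV_7000 kept alongside PTV_6750 | 70 Gy | 70 and 67.5 Gy at once |

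Neither reading of 6.1.1 gives the band 67.5 Gy.

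**5. Size against section 1.0.**
- Replacement, band: BED10 70.725 − 85.725 = −15.0 Gy; 15.0/85.725 = 17.5% lower.
- Replacement, beyond 10 mm: BED10 85.725 − 89.60 = −3.9 Gy (4.3% lower).
- PTV_7000 kept, band: BED3 135.33 − 128.25 = +7.1 Gy (5.5% higher).

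**The case against.** **Section 6.1.1 can be read as coherent by itself.** PTV_6750 would be a single pulled-back high-dose volume that takes the place of PTV_7000. Support for this is real: the second sentence in section 1.0 quoted above speaks of these patients as a whole, the coverage list pairs the two volumes with a slash, the prescription list puts PTV_6750 under PTV_7000, and Appendix E calls 67.5 Gy a high-dose PTV. Against it, Selection of HRT Dose limits the reduction to target within 1 cm. The covariate in 11.2.2 adds the two volumes, which suggests separate parts but could mean whichever was drawn. What stands is that intent is uncertain. The conflict stays, because replacement gives the near target 57.5 Gy, not 67.5 Gy.

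**High-dose coverage is discretionary.** Item g.iv already lets the physician accept less than ideal coverage when mandatory organ limits fail, and a 57.5 Gy band would satisfy the mandatory PTV_5750 coverage. This lowers the weight of the dose differences. It does not tell a planner which volume to draw.

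**A reader might infer that the error raises the airway dose.** That needs PTV_7000 to be kept at 70 Gy in the band. It is a formal possibility but an unlikely plan: the volume is drawn only after the airway limits have failed, and this reading gives no airway relief and assigns two doses to the same distant tissue. The airway D0.03 cm³ limit of 73.5 Gy is mandatory throughout.

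**A reader might also infer that D3 cm³ < 66.25 Gy is a firm mandatory limit that Appendix N wrongly leaves out.** The documents do not support that. Section 6.1.1 lists it as mandatory, but section 1.0 makes only the maximum-dose airway limits mandatory and the volumetric ones ideal. Appendix E labels 66.25 Gy the volumetric limit, and Appendix N checks only D0.03 cm³.

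**Conclusion.** The point holds as a conflict in the operative treatment instruction. Sections 1.0 and 6.1.1 assign 67.5 Gy to regions that do not overlap. On the most coherent literal reading of 6.1.1, the band 5 to 10 mm from the airway is prescribed 57.5 Gy instead of 67.5 Gy (BED10 17.5% lower), and the remaining high-dose target is prescribed 67.5 Gy instead of 70 Gy (BED10 4.3% lower).

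Limits on that size:
- These are prescriptions. The delivered difference in the band would probably be smaller, since the band adjoins a 67.5 Gy volume.
- The geometry is worked along one line and ignores removal by other PRVs.
- The documents do not say how often the PBT limits fail. The range is 0 to all 30 patients planned in 11.3.1.
- The trigger is itself unsettled while the status of the D3 cm³ limit differs between sections.

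The primary test, sample size and power do not depend on this point. On the analysis side it reaches only the exploratory volume covariate in 11.2.2. If PTV_7000 were kept whole, PTV_6750 would be a subset of it and the sum would count that part twice.

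**What to change.** 1. In 6.1.1, for cases where the PBT limits cannot be met, define PTV_6750 as the intersection of PTV_7000 and PBT_1cm at 67.5 Gy, and keep PTV_7000 minus PBT_1cm at 70 Gy. This agrees with Selection of HRT Dose and makes the sum in 11.2.2 well defined.
2. Before that edit, the sponsor should confirm the intent. If one reduced high-dose volume was meant, state that volume in 6.1.1, say what dose the band receives, and correct Selection of HRT Dose.
3. State whether D3 cm³ < 66.25 Gy is mandatory or ideal, and align sections 1.0 and 6.1.1 and Appendix N. Do not add it to Appendix N as mandatory until this is settled.
4. In Appendix E, relabel the 67.5 Gy row. It names bronchial invasion, but the trigger elsewhere is failure to meet the PBT limits.

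The cost is one sponsor confirmation on the volume and one on D3 cm³, a definition line, a table label and the matching text. If patients have already been planned under different readings, their plans need to be identified before the 11.2.2 covariate is used.

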6.2 General Concomitant Medication and Supportive Care Guidelines

Patients should receive *full supportive care*, including transfusions of blood and blood products, erythropoietin, antibiotics, antiemetics, etc., as clinically indicated. Anti-inflammatory or narcotic analgesics may be offered as needed. Medications considered necessary for the patient's well-being may be given at the discretion of the investigator, i.e., chronic treatments for concomitant medical conditions, as well as agents required for life-threatening medical problems, etc. The reason(s) for treatment, dosage, and dates of treatment should be recorded on the flow sheets.

6.3 Duration of Therapy/Study Follow-up

Treatment may continue until the completion of radiotherapy or until one of the following criteria applies:

- Disease progression
- Intercurrent illness that prevents further administration of treatment or ability to present for follow-up visits (i.e. hospitalized)
- Unacceptable adverse event(s)
- Patient decides to withdraw from the study, or further follow-up on study
- General or specific changes in the patient's condition that render the patient unacceptable for further treatment in the judgment of the investigator
- If patients have disease progression or require further radiation treatment outside the protocol, they will be treated at the discretion of their treating physician. They will be followed for local control and survival for 25 months after they have completed their initial radiation.

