5.2 Secondary Outcomes

- 5.2.1 Toxicities will be evaluated per CTCAE Version 5.0 one month following completion of therapy and then every 3 months thereafter until 25 months from completion of radiation therapy.
- 5.2.2 Patterns of progression will be defined as follows: Local progression will be defined as in field progression (see Section 5.1.1); regional progression will be defined as any new regional lymphadenopathy in the hilum or mediastinum that was not included in the gross tumor volume (GTV); distant progression will be defined as any radiographic or pathologic evidence of disease outside the primary tumor and regional lymph nodes, including subsequent pulmonary parenchymal lesions. Progression-free survival will be evaluated by considering the time from registration to progression of disease or death; those who do not experience either outcome will be censored at date of last visit. Overall survival will be evaluated by considering the time from registration to death from any cause; those who do not die will be censored at date of last visit. Progression will be assessed through CT scans administered immediately following treatment and then every 3 months after that, out to 25 months.

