6.0 Treatment Plan

6.1 Study-Related Activities

Activity	Pre- Study ^a	Prior to First Fraction of RT	At Each Weekly Treatment Visit on RT	1 month after RT completion	Every 3 months after 1 month post-RT scan until 25 months after RT ¹
Informed consent	X				
Demographics	X				
Medical history	X			X	X
Concurrent meds	X				
Physical exam	X			X	X
Vital signs ^g	X			X	X
Height ^d , Weight, ^g	X			X	X
Performance Status ^g	X		X	X	X
Tumor measurements ^e	X			X	X
B-HCG ^b	X				
FDG PET/CT Skull Base to Mid Thigh ^j	X				
MRI Brain with contrasti	X				
CT Chest/Abdomen ^c				X	X
Adverse event evaluation ^f Mandatory target coverage/dose constraint	X	X	X	X	X
compliance ^k				: 121:	

^a Pre-study requirements listed in table must be completed within 12 weeks prior to registration.

^b Serum or urine pregnancy test (women of childbearing potential). This must be completed within one week prior to initiation of radiotherapy for women of childbearing potential. For our purposes postmenopausal women are defined as women over the age of 45 years old with at least 12 months from their date of last menstruation.

^c CT Chest/Abdomen will be with contrast unless the patient has a documented contraindication to IV CT contrast (ie inadequate renal function or anaphylaxis). The scan must include the entire bilateral lungs, liver, and bilateral adrenal glands. CT Chest/Abdomen/Pelvis is also acceptable.

^d Height measured at pre-study only

e See Appendix Q

f See Appendices F and G

g See Appendix L

^h See Appendix C

¹ If MRI is contraindicated, CT Head with contrast is also acceptable.

^j National guidelines indicates a PET scan is good for 3 months (12 weeks).

^k See Appendix N

¹For all follow-up imaging and clinic follow-up time points above, a flexibility window of +/- 8 weeks is allowed.

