6.4 Duration of Follow Up

Patients will be followed for a minimum of 30 days after the last radiation therapy fraction is administered for adverse events monitoring, unless otherwise specified in this section of the protocol. A different time frame may be longer but not shorter than 30 days unless a specific scientific rationale is presented to suggest that a shorter window can be used to identify events. Follow-up for serious adverse events and mortality after the last study dose is administered will take place during the routine clinic visits that the patient will have during the 30 day follow-up window (Also referenced in Appendix D). If no visit occurs during this window, a phone call confirmation should be made to the patient to determine vital status and whether any adverse events and in particular, Grade 4 unexpected adverse events occurred during that window of time and recorded on Appendix F.

Patients will be followed 25 months or until death after the last study radiation treatment for monitoring survival study endpoints.

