6.5 Criteria for Removal from Study

Patients may be removed from study when any of the criteria listed in section 6.3 applies.

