11.2 Analysis of Secondary Objective

- 11.2.1 We will compute the proportion of the sample developing any toxicity of grade 2 or higher over the 25 months, and construct a corresponding 95% confidence interval.
- 11.2.2 We will compute proportions of patients who have experienced local progression by 13 months (1 year following first post-radiotherapy scan) and by 25 months (2 years following first post-radiotherapy scan), and will also compute the same two proportions considering regional progression, distant progression, and any (of the 3 categories) progression. We will construct 95% confidence intervals around these proportions. Those patients for whom we are unable to determine progression status at 1 and 2 years (e.g., because they do not return for the necessary scans, or because they die without evidence of progression) will be left out of these analyses. We will evaluate PFS and OS first using the Kaplan-Meier lifetable method, and will estimate median survival and corresponding 95% CIs; we will also explore simple Cox proportional hazards models of each of these survival outcomes, to examine the predictive influence of variables such as age, gender, ECOG performance status, stage at diagnosis, PTV 7000+6750 volume, and PTV 5750 volume. Patients who are lost to follow-up will be censored at that time in these analyses.

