11.6 Interim Analysis Plan

No formal interim analysis is planned; however, if 5 patients develop Grade 4 or 5 bronchial fistula, bronchopulmonary hemorrhage, esophageal fistula, hemorrhage or perforation as defined by CTCAE version 5.0, the study will be halted. Patients who have known in-field progression of disease or new or

progressive disease involving the structure that develops the Grade 4 or 5 toxicity prior to toxicity development will not be counted.

References

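### Sections 6.3 and 6.4 conflict with 5.2.1 on toxicity follow-up after progression or further radiation, and 11.2.1 has no rule for toxicity arising after later therapy

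*Combined protocol and SAP*

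**What the plan says.** The last bullet of section 6.3 is the only rule written specifically for patients who progress or need radiation outside the protocol: "They will be followed for local control and survival for 25 months after they have completed their initial radiation". It names two things to follow, and toxicity is not one of them.

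Section 6.4 applies to all patients. On adverse events it says: "Patients will be followed for a minimum of 30 days after the last radiation therapy fraction is administered for adverse events monitoring", unless the section specifies otherwise. On the longer period it says: "Patients will be followed 25 months or until death after the last study radiation treatment for monitoring survival study endpoints". Section 6.5 adds: "Patients may be removed from study when any of the criteria listed in section 6.3 applies". Disease progression is one of those criteria.

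Other parts of the protocol describe a longer toxicity follow-up. Section 5.2.1 states: "Toxicities will be evaluated per CTCAE Version 5.0 one month following completion of therapy and then every 3 months thereafter until 25 months", counted from completion of radiation. The 6.1 calendar has a column headed "Every 3 months after 1 month post-RT scan until 25 months after RT", in which adverse event evaluation is marked. Neither mentions progression.

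Two analyses use these data. Section 11.2.1: "We will compute the proportion of the sample developing any toxicity of grade 2 or higher over the 25 months", with a 95% confidence interval. Section 11.6 halts the study "if 5 patients develop Grade 4 or 5 bronchial fistula, bronchopulmonary hemorrhage, esophageal fistula, hemorrhage or perforation". It does not count patients who already had known in-field progression, or new or progressive disease in the structure that develops the toxicity.

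**The concern.** Fistula, hemorrhage and perforation are the events that the background section uses to justify the airway and esophageal constraints and that the halting rule counts. Section 11.2.1 needs toxicity over 25 months in the whole sample, but the one rule specific to patients who progress does not mention toxicity. A coordinator following 6.3 and 6.4 could reasonably stop grading toxicity at progression. A coordinator following 5.2.1 would continue. The same trial could then hold toxicity data of different depth for different patients, and an analyst cannot later recover events that nobody graded.

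Continuing to grade raises a second question. Section 11.2.1 counts any toxicity of grade 2 or higher, with no rule on attribution, censoring or later treatment. Toxicity caused by radiation outside the protocol, or by the later systemic therapy that 3.1.5.1 permits, would be reported as part of the profile of the study regimen.

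**Working it through.** **Plan figures.** This point disputes none of them. The sample size in 11.3 reproduces: n = [(1.645 + 0.842) × √(0.5 × 0.5) / (0.75 − 0.50)]² = 24.7, so 25; and 25 / (1 − 0.15) = 29.4, so 30 recruited. The 30 is used below.

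**Step 1. The rules side by side.**

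| Section | Applies to | Toxicity follow-up |
|---|---|---|
| 6.3, last bullet | Progression or further radiation | Not named; local control and survival to 25 months |
| 6.4 | All patients | 30-day minimum; 25 months tied to survival endpoints |
| 6.5 | Any 6.3 criterion | Removal from study permitted |
| 5.2.1 | No exception stated | CTCAE every 3 months to 25 months |
| 6.1 calendar | No exception stated | Adverse event evaluation to 25 months |
| 11.2.1 | The sample | Uses any grade 2 or higher event over 25 months; no rule for unassessed patients |
| 11.6 | Patients without prior in-field progression or disease in the affected structure | Uses listed grade 4–5 events |

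In the text available to me, the calendar's adverse event row runs together with the dose-constraint row. The mark in the last column can sensibly belong only to adverse events.

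**Step 2. Two readings.** If 6.3 limits follow-up, toxicity after progression is not required. If 5.2.1 governs, it is required to 25 months and nothing is lost. The text does not say which prevails.

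**Step 3. What 11.2.1 could lose if 6.3 limits.** The measure is whether a patient ever has grade 2 or higher toxicity, so a patient with such an event before progression already counts. Only first events after progression can be lost. Assume that unassessed patients stay in the denominator as event-free and that progressors and others have the same grade 2 or higher risk. Then:

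relative loss = q × l,

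where q is the share who progress and l is the share of progressors' first events that come after progression. For q, 11.3 implies 25% in-field progression at two years under the target and 50% under the null; regional and distant progression would add to this. The documents give no value for l, so I assume 10% to 50%.

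- Low: 0.25 × 0.10 = 0.025, a relative loss of 2.5%.
- High: 0.50 × 0.50 = 0.25, a relative loss of 25%.

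This shows sensitivity and is not an estimate. If 5.2.1 is followed, the loss is zero.

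**Step 4. What 11.6 could miss if 6.3 limits.** The exposed patients are those with regional or distant progression away from the affected structure, and those given further radiation without excluded progression. Let p be the true rate of countable events and m the share not ascertained (assumed; the documents give no value). With X ~ Binomial(30, p(1 − m)), the chance that X reaches 5 is:

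| p | m = 0 | m = 10% | m = 25% | m = 50% |
|---|---|---|---|---|
| 5% | 0.016 | 0.010 | 0.005 | 0.001 |
| 10% | 0.175 | 0.128 | 0.070 | 0.016 |
| 15.4% | 0.500 | 0.404 | 0.261 | 0.077 |

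Section 9.1.3 puts severe airway injury below 5%. The 15.4% is the grade 5 rate in the ultracentral SBRT study described in section 1.0. It comes from a different regimen and serves only as an upper scenario; 10% is an assumed midpoint. Because 11.6 already removes in-field progressors, m covers only the remaining groups.

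**Step 5. If 5.2.1 governs.** Events after later radiation or systemic therapy enter the 11.2.1 numerator. The adverse event log in Appendix F records attribution, but 11.2.1 does not use it. The effect is upward, and the documents give nothing from which to size it.

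**The case against.** The strongest reply is that toxicity follow-up is already required for everyone. Section 5.2.1 and the calendar make no exception, and Appendix D requires all adverse events in any enrolled patient to be entered in the institutional system. The 6.3 bullet sits in a list about how long treatment lasts and nowhere says that other follow-up stops. It can be read as a floor that keeps progressors under observation for the efficacy endpoints. In addition, esophagitis and pneumonitis tend to appear early on the protocol's own account (9.1.2 and 9.1.4), so many first grade 2 or higher events would precede progression.

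All of this stands, and it limits what can be said. A reader might infer that toxicity collection ends at progression and that late toxicity is therefore understated. The documents do not support that: they disagree with each other, and one side of the disagreement gives complete collection. A reader might also scale down the 15.4% to obtain a reported rate. That would apply a fatal-event rate from another regimen to an ever-grade-2 proportion, and it would ignore the progressors that 11.6 leaves out. Nor is a downward direction certain, because later therapy can push the proportion up. Section 11.2.1 also does not state that unassessed patients count as event-free; that is an assumption in Step 3.

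The reply does not remove the conflict. The 6.3 bullet is the specific rule, and 6.4 points the same way. Appendix D requires entry of events but schedules no assessment, and its reporting window to the safety committee closes 30 days after the last treatment. The Appendix G form asks only about the preceding 30 days, while visits are three months apart. For late events, the scheduled CTCAE evaluation is the main source, and it is the item left unclear.

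**Conclusion.** The point holds as an inconsistency that should be reconciled, with a related gap in 11.2.1. Sections 6.3 and 6.4 do not agree with 5.2.1 and the calendar on toxicity follow-up after progression or further radiation. Loss of first grade 2 or higher events from 11.2.1, and of countable events from 11.6, is a risk that depends on staff reading 6.3 as limiting. It is zero if 5.2.1 is followed. In that case 11.2.1 instead mixes study toxicity with toxicity arising after other treatment.

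Neither effect can be sized from the documents. The ranges in the working rest on assumed timing, an assumed share of unascertained events, and unassessed patients being kept as event-free. The sample size, power and significance level are unaffected. The change is worth making because it is cheap and because toxicity that was never graded cannot be reconstructed at analysis.

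**What to change.** 1. In the last bullet of 6.3, add toxicity to what is followed: local control, toxicity (CTCAE v5.0, on the 5.2.1 schedule to 25 months) and survival.
2. Reconcile 6.4 with this, so that the 30-day minimum is not read as the end of toxicity follow-up and the 25 months are not tied to survival alone. State in 6.5 how removal for a 6.3 criterion fits with continued toxicity follow-up.
3. Record the start date of any later thoracic radiation or systemic therapy. The forms shown have no field for it, and the concurrent medication form (Appendix M) is completed only before treatment.
4. In 11.2.1, report the proportion with grade 2 or higher toxicity twice: overall, and counting only events dated before such therapy began. Show how many patients started later therapy and when, because they have a shorter window in the second figure.

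The cost is one phrase in 6.3, matching edits in 6.4 and 6.5, a date field, one extra reporting line, and slightly more data entry at visits already scheduled. The reported toxicity rate may be slightly higher. Treatment and sample size do not change.
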